## D7. Data Sources

To test our hypotheses, we need data from multiple sources (Table 9). (Please refer to the power calculations for a description of over sampling to account for dropout and non-response). Data will be maintained and analyzed (using SAS, SAS Institute, Cary, NC) by [name] under the supervision of [name], our statistician.

### 1) Interest Survey and Practice Baseline Survey – Important

covariates including practice organizational structure, workload, reimbursement, and patient population will be available. Because time limitations are a frequently-reported barrier, self-report of practice workload may be an important predictor of the intervention success.

### 2) Hygienist Internet Portal (Refer2Quit) – We will collect two

datasets from the provider Internet site – the Basic Profile Questionnaire – Providers (BPQ-Pr) and Participation Tracking. Covariates including provider demographics, smoking counseling attitudes, and self-reported counseling of individual providers will be collected using the BPQ-Pr when providers first access HI-QUIT.

We will also track website activity to assess intensity of participation. We will define four components of participation including frequency of participation (number of logons), total participation (number of pages viewed, cumulative session time), breadth of participation (use of various components – cases, toolbox, provider reports, etc.), and consistency of participation (participation in all months) (see Table 3). We will use these data in analysis to assess mediation of level of participation on outcomes.

3) **Patient exit cards (Hypothesis 1)** – We will use patient exit cards to assess providers' performance, focusing on **Refer**. Fiore et al. have used patient exit interviews to assess implementation of tobacco cessation counseling and treatment in previous clinical trials. Provider self-reports often overestimate actual activities, and the National Committee for Quality Assurance's Health Plan Employer Data and Information Set (HEDIS) has recently incorporated a patient survey-based measure of tobacco counseling. As discussed above, patients will complete exit cards as they leave their appointment.

4) **Patient Website and information prescriptions (Hypothesis 2)** – We will use the patient website to track number of patients who participate per practice for Hypothesis 2. The number who are referred will be collected by the website in the intervention group, but we must use the information prescriptions in the control (see Section D8, Main Evaluation Measures). In addition, as each patient accesses the intervention or control websites, we will collect a Basic Profile Questionnaire – Smokers (BPQ-SM). The BPQ-SM will be used to

Table 9: Key Data Elements, Their Data Sources, and Hypotheses for quantitative analyses	Interest Survey	Practice Surveys	Provider Website	Patient Exit cards	Patient Website	Patient Follow-ups
Practice Structure (# MDs)	B					
Type of Practice	B					
Internet Access	B					
Level of Interest	B					
Patients per Week	B	B,F				
Provider Demographics	B	B				
Proportion of Patients who Smoke	B			B,F		
Outcome Expectation - Counseling			B,F			
Patient contact (hours/week)	B		B,F			
How Busy is Practice?		B,F				
Practice Location		B				
Perceived Barriers to Counseling			B			
Use of HI-QUIT (Providers)			F			
Pre-intervention tobacco counseling				B		
Post-intervention Refer				H1		
Use of website (Patients)					H2	
Type of Tobacco Use				B	B	F
Patient demographics					B	F
Level of Addiction					B	F
Medical Comorbidities					B	F
Past Quit History					B	F
Readiness to Quit				H3		H3
Quit Attempts						H3
Tobacco Prolonged Cessation*						H3

B= baseline covariate, F = Follow-up; H1= Outcome for Hypothesis 1; H2= Outcome for Hypothesis 2; H3= Outcome for Hypothesis 3; \*validated by cotinine

Principal Investigator/Program Director (Last, First, Middle): DPBRN c/o [name]

target content of the website to individual patients and as covariates in our analysis of cessation rates of those who participate in the website (H2). Using tracking data, we will also create variables related to participation similar to those of providers described above.

**5) Patient follow-up assessment (Hypothesis 3)** – Tobacco cessation behaviors will be assessed by follow-up telephone interviews at six months from website enrollment. We will have three measures of tobacco cessation behavior: 1) Tobacco cessation, 2) Quit Attempts, and 3) Stage of Change (Transtheoretical Model). As recommended in the new standard criteria for evaluation smoking cessation trials, smoking cessation will be validated at six months using cotinine. We have had experience in previous studies in validating cessation by using mailed salivary cotinine measures. Currently, we are using Salimetric’s mailed salivary cotinine test.

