**D. RESEARCH METHODS****D1. Overview, Task List, and Timeline**

Our task list (Table 6) is organized into 6 categories: 1) intervention refinement and programming; 2) usability testing; 3) recruitment and retention of dental practices; 4) intervention maintenance; 5) data collection; and 6) analyses. As discussed in Section A, we evaluate the process of care.

The combination of the patient and hygienist internet interventions is entitled HI-QUIT (hygienists' internet quality improvement in tobacco cessation). HI-QUIT is conceptualized in two components: Refer2Quit and Decide2Quit (See Figures 4 and 5). Major innovations are the microsystem integration of the patient referral portal (Refer2Quit) and the hygienist education system. We will conduct a randomized controlled trial (RCT) to ascertain the efficacy of this multi-modal intervention in improving smoking cessation processes of care and patient outcomes. In relation to the smoking cessation impact of HI-QUIT, this trial is defined as a cessation-induction study – a test of treatment to prompt cessation among all smokers, including those who are not currently trying to quit.

Studies of complex microsystem interventions are inherently complex and require detailed evaluations. In addition to our quantitative hypothesis-driven analysis, we will also conduct a secondary process analysis case-comparison of intervention practices with varying rates of adoption of HI-QUIT. The proposed intervention is designed to have a layered effect – changing hygienist performance (including advising smokers to quit and referring them to a self-management website) and also patient behavior (including going to use the website and ultimately quitting smoking). Thus, our analyses are designed to understand the intervention from each of these “layers” – from the patient and hygienist perspective.

Table 6: Task List		Study Months	1.Intervention Refinement	2.Usability Testing	3.Recruitment - Retention	4.Intervention Maintenance	5.Data Collection	6.Analyses
1	Finalize recruitment plan and website plan	1-3	X	X				
2	Program Refer2Quit hygienist website	2-7	X					
3	Program Decide2Quit intervention patient website	2-7	X					
4	Conduct final usability testing by patients and hygienists	6-7		X				
5	Finalize website based on usability tests	7	X					
6	Develop and finalize investigators web “admin” portal	7	X	X	X			
7	Activate HI-QUIT	7				X		

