### D3. The CONTROL – information prescriptions to refer to patients

#### 1. Hygienist Control – Information Prescriptions

In planning this proposal, we considered several potential controls as suggested by the framework for evaluating complex

interventions. In DTC.Net, we are currently using a wait-list control group. Control providers will have access to the full intervention after data collection is complete. Thus, control hygienists are delivering “usual care.” However, for this intervention, we felt that a wait-list control ignores other recent advances in provider referrals to self-management in smoking cessation (i.e.: information prescriptions).

Also, although we have not had differential attrition in the wait-list control, compared with intervention, in DTC.Net, anecdotally, control providers have expressed concerns about having “nothing new” to provide to patients. We are concerned about the threat of long-term wait-listing to overall retention in the control group. Specifically, we want to test the uniqueness of the integration clinical microsystem intervention. After consideration, we have chosen a more active, symmetric control reflecting recent offline research into provider referrals. Thus, our control group provides parallel interventions – for providers and then patients – that are *not* integrated.

We have chosen an “information prescription” control. Providers in the control group will be provided preprinted pads of “information prescriptions” with their office information, motivational messages for patients, a space for the provider to sign, and the control website address.

The information prescription pads also have an important role in our analysis. The pads will have numbered leave-behind receipts used to tally the number of referrals issued. These pads will be collected from the control practices to obtain an accurate account of the number of patients referred. The control group will not have access to 1) HI-QUIT Help Desk, 2) Refer2Quit portal at the point of care; 2) Feedback Reports of patient activity; 4) automated email reminders for patients and providers; 5) HI-QUIT content updates and linking functions.

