**Randomization** - We will use an online randomization algorithm developed by [name]. Once providers review the recruitment and consent information online, those that agree to participate will proceed to update their contact information and then click on a link [I AGREE TO PARTICIPATE]. Once they click on this link, a program on the server will randomize their practice to the control or intervention arms in blocks of six to assure roughly equal numbers. Thus, the first provider who logs on will determine the randomization status for all providers and staff within the entire practice. This ensures that the level of randomization is the clinical microsystem (dental practice).

**Anticipating attrition** – Although data are not complete for follow-up in DTC.Net, we currently have data from 143 of 190 randomized practices (76%) and anticipate a final participation rate at follow-up of 80%. Using these numbers, we plan to recruit 100 practices to the “interested” pool, to obtain 80 practices to be randomized. For power calculations, we have estimated that a range from 30 to 40 practices per arm will complete follow-up data collection. If the practices withdraw from the study prematurely, we will retain their data as for an “intention to treat” analysis. We will compare practices that withdraw with those that do not.

6. Recruitment Phase 2: Patient Recruitment for Outcomes Assessment - Patients will be recruited to participate in the study in two ways, as determined by our analysis plan. First, patients will be recruited to assess providers using brief exit card surveys completed as they are discharged from their clinic appointment. Second, patients will be enrolled as they login to the patient website.

**Patient Recruitment Part 1: (Exit Card Surveys)** - For *Hypothesis 1* (Processes of Care – including the proportion of patients who are referred to self-management resources will be greater in HI-QUIT practices compared with control practices) we need a measure of provider performance. Provider reports of smoking counseling over-estimate and chart abstraction under-estimates performance. Patient reports of provider behavior have also been used. The Health Plan Employer Data and Information Set (HEDIS) performance measurement has adopted patient-report of provider tobacco cessation advice using phone

Principal Investigator/Program Director (Last, First, Middle): DPBRN c/o [name]

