providers and patients. Thus, our analysis should be designed to evaluate these sources. To this end we will use multilevel modeling to explicitly evaluate the sources of variability in HI-QUIT usage.

Analyses for H1: We will assess differences between intervention and control in three ways.

As our **primary analysis**, we will use patient-level data and multilevel modeling to account for practice-level effects and adjusting for the complex effects of patient and provider variables in multivariable analyses. We have chosen this as the primary analysis for two reasons: 1) because this analysis represents a detailed understanding of the effects of the clinical microsystem intervention, and 2) because we have empirically-driven intraclass correlation coefficients to guide our power calculations.

Thus, to test the overall effect of HI-QUIT, we will use data from all post-intervention evaluation time points together. The hypothesis will be tested by using logistic regression, using patient-level data and incorporating practice-membership as a design factor. An important consideration in handling correlated data resulting from group-randomization is properly accounting for the correlations in the analysis. For example, positive correlations will result in the underestimation of standard errors of the between-practice effects and overestimation of the standard errors of the within-subject effects. Generalized Estimating Equations (GEE), specifically designed for correlated outcomes that can be modeled with a generalized linear model (GLM) including logistic regression, will be used. PROC GENMOD can easily accommodate GEE methods adjusting for clustering. For multivariable analyses logistic regression will be used again, with accounting for clustering. These models will allow adjustment for patient and practice variables described in Section D7. We will also test the hypothesis using data from each individual time point.

**Hypothesis 2: The proportion of patients referred who GO to the patient self-management website will be larger in HI-QUIT practices (40%) compared to control practices (20%).**

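### Provider attitudes and self-reported counselling are collected after the practice is randomised, so they cannot serve as baseline covariates in the provider-adjusted H1 model

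*Protocol*

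**What the plan says.** **Collection.** D7, item 2 (Hygienist Internet Portal, Refer2Quit) draws two "datasets from the provider Internet site – the Basic Profile Questionnaire – Providers (BPQ-Pr) and Participation Tracking". Provider demographics, counselling attitudes and "self-reported counseling of individual providers will be collected using the BPQ-Pr when providers first access HI-QUIT". D1 defines the term: "HI-QUIT is conceptualized in two components: Refer2Quit and Decide2Quit".

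**Randomisation.** In D5 a provider reviews the recruitment and consent information online, updates contact details and clicks an agreement link. "Once they click on this link, a program on the server will randomize their practice to the control or intervention arms". As a result, "the first provider who logs on will determine the randomization status for all providers and staff within the entire practice".

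**Control access.** D3.1 states: "The control group will not have access to 1) HI-QUIT Help Desk, 2) Refer2Quit portal at the point of care". It also withholds feedback reports and automated emails to providers.

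**Table 9.** Outcome Expectation is marked as baseline and follow-up, and Perceived Barriers as baseline, both under Provider Website alone.

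**Use.** D9, Analyses for H1, describes the primary analysis as multilevel modelling of patient-level data, "adjusting for the complex effects of patient and provider variables in multivariable analyses". Later in the same section the multivariable models are said to allow adjustment for patient and practice variables from D7.

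**Participation.** On website activity tracked in the provider portal, D7 says: "We will use these data in analysis to assess mediation of level of participation on outcomes".

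**The concern.** A covariate can safely be adjusted for in a randomised comparison when it is fixed before allocation and measured in the same way in both arms. The provider attitude items meet the first condition nowhere in the text, and it is unclear whether they meet the second.

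An intervention that educates, prompts and gives feedback to providers can plausibly change their views on counselling and its barriers, and how much counselling they report. Adjusting the H1 contrast for such answers can remove part of the effect being tested. It also favours providers willing to log on and complete a form, and that willingness may differ by arm because control providers receive no automated reminders. If control answers do not exist at all, a model containing them has no control data.

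This is a matter of data collection as well as analysis. An analysis plan written later can drop the items, but it cannot recover a baseline that was never taken.

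**Working it through.** No treatment-effect figure follows from this point, so the check traces source, timing and arm access.

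**1. Is any stated figure affected?** The D10 sizing for H1 uses 12% against 24%, two-sided 0.05, 80% power, ICC 0.15 and 66 smokers per practice.
- The two-proportion formula gives 160 per group without continuity correction and 176 with it; the plan prints 176.
- Design factor: 1 + (66 − 1) × 0.15 = 10.75.
- Adjusted n: 176 × 10.75 = 1,892.
- Practices: 1,892 / 66 = 28.7, rounded up to 29 per arm.

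These match the plan. No covariate enters the calculation, so the point leaves it unchanged.

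**2. Order of events.** D5 places initial consent, the collection of provider names and the run-in before providers reach the website. Before the randomising click it lists only reviewing the recruitment and consent information and updating contact details. The provider questionnaire is not listed there. It is tied to first access to HI-QUIT, which is itself the allocated intervention. For the first provider it therefore follows the click, possibly by a short interval. For every other provider in the practice it is certain that the arm is already set.

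**3. Which variables have no pre-randomisation source?**

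| Variable | Source in Table 9 or D7 | Pre-randomisation source? |
|---|---|---|
| Provider demographics | Interest Survey, Practice Surveys (also listed in the questionnaire, D7) | Yes |
| Patient contact hours | Interest Survey and Provider Website | Yes |
| Pre-intervention tobacco counselling | Exit cards, run-in | Yes, both arms |
| Outcome Expectation | Provider Website only | No |
| Perceived Barriers | Provider Website only | No |
| Self-reported counselling | Questionnaire only (D7; no row in Table 9) | No |

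**4. Are there control values?** D7 puts the questionnaire under Refer2Quit, and D3.1 denies that portal to controls. D7 item 4 says the patient questionnaire is collected on the intervention or control website, whereas item 2 names only HI-QUIT for providers. Against this, Section E has providers review an intervention or a control website, and its risk section has providers using both kinds of site. No section puts the provider questionnaire on the control site, and none says it is left off. The text does not settle the matter.

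**5. What happens in the H1 model?** There are two cases if the last three variables in the table are included.
- *Collected in both arms after allocation:* the treatment coefficient is conditional on variables that treatment may have moved.
- *Collected only through Refer2Quit:* a complete-case fit keeps 0 of 40 control practices, and the treatment coefficient cannot be estimated.

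If they are left out, neither problem arises.

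**6. Participation intensity.** D7 counts use of cases, toolbox and provider reports. Controls have no Refer2Quit portal and no feedback reports. Setting them to zero would tie the measure to the arm and, within the intervention arm, to provider motivation. Table 9 marks provider use of HI-QUIT as follow-up, so it is not offered as a baseline covariate. The difficulty lies in calling the analysis mediation.

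**The case against.** The strongest reply is that the gap is narrow and the plan never commits to the harmful model. Table 9 supplies demographics and contact hours from the Interest Survey, and it takes baseline counselling, the natural H1 covariate, from run-in exit cards in both arms. The D9 sentence that refers to D7 speaks of patient and practice variables and is permissive. The sentence on provider variables names neither the questionnaire nor D7. The clustered test of assignment needs none of these items. Covariate lists and missing-data rules commonly belong in the SAP. The first provider answers close to the moment of randomisation, with little exposure to the arm.

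Much of this stands, and it sets the limits of the point. It does not remove the core. Two items are labelled baseline although their only source comes after allocation, and the primary H1 analysis is described as adjusting for provider variables. D9's two descriptions of the adjustment set do not agree. Later providers do not answer at the moment of randomisation.

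A reader might go further and infer that 40 of the 80 practices have no provider profile, so that the adjusted H1 model cannot be fitted. The documents do not establish this. Section E gives control providers a website, and the plan specifies neither complete-case analysis nor a covariate list containing these items. Nor does it follow that all provider covariates are compromised, since demographics and contact hours have an earlier source.

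**Conclusion.** The point holds for Outcome Expectation, Perceived Barriers and questionnaire self-reported counselling. As scheduled, they are post-allocation measurements, and they should not be treated as baseline in a model that estimates the H1 effect. Whether control values exist is left open by the text, and the conflicting statements need to be reconciled.

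The size is conditional. If the items are used and exist in both arms, the adjusted effect may be biased by an amount the documents give no basis for calculating. If they are used, exist only in the intervention arm and are analysed by complete case, the treatment coefficient cannot be estimated. If they are not used, H1 is unaffected. The assumptions are that first access to HI-QUIT follows the agreement click, as D5 and D7 read together, and that the provider variables in D9 may include the questionnaire items.

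**What to change.** Preferred: give the provider questionnaire in both arms before allocation. The first provider completes it on the online recruitment and consent pages, ahead of the agreement click. The other providers, whose names and emails D5 already collects at step 3, complete it during the run-in. Use only these values in the H1 adjusted model, and correct D7 and Table 9 to match.

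Alternative: keep the present timing, limit H1 adjustment to pre-randomisation variables available in both arms (Interest Survey and run-in exit cards), and stop marking the website attitude items as baseline.

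Under either option, state in D7 whether the questionnaire is given to control providers, make D9's two descriptions of the adjustment set agree, and describe Refer2Quit participation as dose-response within the intervention arm in place of mediation.

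Cost: the preferred option reuses an existing form but adds a short task before randomisation for each named provider, across the roughly 100 interested practices that D5 plans to recruit. The alternative costs only wording, and gives up attitude covariates for H1.

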**D8. Main Evaluation Measures**

As depicted in Figure 4, HI-QUIT is designed to have a sequence of effects on the process of care within each clinical microsystem. Thus, we have designed our main evaluation to assess several key areas of influence that we have abbreviated as **Refer -> GO -> QUIT**. For our hypotheses, we have three primary dependent variables. Each of the outcomes is collected at the patient level and is used to create a proportion. The first link in the chain of evaluation is of course to assess the performance of the provider. We will use the exit cards to assess the proportion of smokers who are referred. This is assessed at discrete time points (Patients recruited in 3 cohorts at intervention Time 0 (I0) (pre-intervention), I0 + 6 months, I0 + 12 months,).

This analysis is solely to assess provider performance and data are collected from patients anonymously. The proportion of smokers who are referred who GO to the website (H2), and the subsequent

Table 10: Dependent (outcome) variables (Refer -> GO -> QUIT)					
Label	Question	Source	Collected	Numerator	Denominator
Refer (H1)	During your provider’s visit TODAY did anyone: Refer you to Decide2Quit* - a website with information about tobacco?	Patient Exit Card	Discrete Intervals (baseline, 6 and 12 Months)	Number Referred	Number of Smokers
GO (H2)	Proportion of patients from the practice who log onto website	Website tracking and information prescriptions	Continuous	Number who GO	Number Referred ‡
QUIT (H3)	Do you currently smoke cigarettes (smoked even 1 puff in the last 7 days)?	6 month survey†	Continuous	Number who QUIT	Number Referred ‡
* control website for Controls; † validated using mailed cotinine saliva kit. ‡ Assessed by web tracking in intervention, in control by leave-behind receipts from information prescriptions					

proportion who QUIT (H3) are assessed continuously throughout the study. For H2, the numerator is the number who GO, as tracked by HI-QUIT and the control website. The denominator is the number referred. Because of the nature of the Internet versus paper referral system, by definition, the continuous assessment of the number of patients who are referred is different by study arm. Our interest in H2 is the proportion of patients referred who logon, or ‘GO’, to the website (% who go = number who visit/number referred). In the intervention group, the webserver collects the number of patients entered into the system per practice (i.e.: denominator, the number referred). In the control group, patients are not entered into an electronic system, but are referred using an “information prescription.” In both groups, the intervention and control websites collect the number of patients who visit the site. Thus, assessment of the numerator is the same, but assessment of the denominator is systematically different by arm. We have developed protocol for more accurately measuring the denominator and the number referred in the control group by using the information prescription pads with a leave-behind notation of when the patient was referred. We will collect the empty prescription pads from the control practices to assess the number of patients referred for the denominator.

For H3, the dependent variable is point prevalent cessation (QUIT). Smoking cessation trialists have recommended assessment of smoking cessation in randomized trials using both measures of 1) point

Principal Investigator/Program Director (Last, First, Middle): DPBRN c/o [name]

prevalence cessation, and 2) continuous or sustained abstinence. Continuous abstinence is preferred when participants have a defined quit date and face-to-face meetings with staff. The HI-QUIT trial is defined as a **cessation-induction study** – a test of treatment to prompt cessation among all smokers, including those who are not currently trying to quit. Provider advice to quit smoking and telephone quitlines are classic examples of cessation induction trials. Like most cessation-induction studies, patients in our study will come into contact with the intervention at irregular intervals after their initial office visit and we will encourage repeated exposures (website visits) in the intervention. As Hughes and colleagues for the Society for Research in Nicotine and Tobacco workgroup on measurement note, point prevalence cessation is often the best measure for cessation-induction trials. We will also collect a measure of prolonged cessation.

Cotinine biochemical verification: In 2002, the SRNT Subcommittee on Biochemical Verification published recommendations and evidence to aid the decision-making in choosing biochemical verification. This article divided studies into clinic-based trials (usually with less than 500 participants) where misclassification is higher and the need for biochemical verification is high and participation in biochemical verification is also high, versus population-based studies where misclassification is low and biochemical verification is less needed, and is in fact less feasible (with non-response rates up to 70%). In planning the study, we feel that HI-QUIT is closer to a clinic-based trial. The connection to the clinical microsystem makes this study more intense than public health interventions and may change the demand characteristics. To increase participation rates for the mailed salivary cotinine, we will provide an additional incentive of \$50 for completing this sample. However, we acknowledge that not all patients may complete cotinine validation by mail. For patients who self-report quitting at six months, but fail to return their cotinine saliva sample, we will use their self-report data, acknowledging that those who do not return their cotinine sample will be more likely to mis-report cessation. We will carefully assess for differential misclassification comparing intervention and control. First, we will compare participation rates for returning the cotinine sample by intervention and control. Next, we will assess self reported cessation among those that do and do not return the cotinine sample (comparing intervention and control). Finally, we will compare the misclassification rates among those that did return the sample (again intervention vs. control). If differences are detected, this would represent a case of non-ignorable missing data. Using these rates, we will conduct sensitivity analyses to assess the impact of differences in participation and misclassification on our main outcome and use pattern mixture approaches to assess how much our main analysis might change.

**D9. Analysis Plan:** For each practice, HI-QUIT is available for 20 months (see Figure 3, section D1). We plan to assess the impact of the intervention throughout this interval.

Unit of Inference. Our unit of randomization is at the practice level, but, all our outcomes are assessed at the patient level. With data at the patient level, we have the flexibility to set our unit of inference at the practice level, or at the patient level (with the second two using modeling techniques to account for clustering). We have carefully considered the unit of inference for each hypothesis. A recent article by Donner discusses the unit of inference and notes that it is often most appropriately set at the unit where the effect is most important to the investigators. As discussed, the HI-QUIT intervention is designed to target all aspects of the clinical microsystem (patients, providers, and processes within the practice). Both dentists and hygienists will have a role in implementing the system and it is anticipated that the roles of dentists and hygienists in Refer2Quit will vary from microsystem to microsystem – although we anticipate that hygienists will usually be the driving force behind Refer2Quit. Considering the unit of inference is particularly important for Hypothesis 1, assessing rates of referral. There are multiple sources of effects, including the providers and patients. Thus, our analysis should be designed to evaluate these sources. We will use hierarchical modeling to explicitly test the sources of variance in using HI-QUIT.

**Hypothesis 1: The proportion of patients Referred to self-management resource websites will be larger in HI-QUIT practices (24% of smokers) compared to control practices (12% of smokers).**

Data Definitions for Hypothesis 1 (H1): The main dependent variable is the dichotomous outcome of “Refer”, indicating whether a patient is referred, as ascertained by the patient exit cards at discreet intervals (6 and 12 months). As secondary dependent variables, we will also test differences in the other provider performance measures assessed by the exit card (screening for tobacco use, provider advice to quit). The primary independent variable is assignment to intervention or control. Considering the unit of inference is particularly important for Hypothesis 1 (assessing rates of referral). There are multiple sources of effects, including the

Principal Investigator/Program Director (Last, First, Middle): DPBRN c/o [name]

providers and patients. Thus, our analysis should be designed to evaluate these sources. To this end we will use multilevel modeling to explicitly evaluate the sources of variability in HI-QUIT usage.

Analyses for H1: We will assess differences between intervention and control in three ways.

As our **primary analysis**, we will use patient-level data and multilevel modeling to account for practice-level effects and adjusting for the complex effects of patient and provider variables in multivariable analyses. We have chosen this as the primary analysis for two reasons: 1) because this analysis represents a detailed understanding of the effects of the clinical microsystem intervention, and 2) because we have empirically-driven intraclass correlation coefficients to guide our power calculations.

Thus, to test the overall effect of HI-QUIT, we will use data from all post-intervention evaluation time points together. The hypothesis will be tested by using logistic regression, using patient-level data and incorporating practice-membership as a design factor. An important consideration in handling correlated data resulting from group-randomization is properly accounting for the correlations in the analysis. For example, positive correlations will result in the underestimation of standard errors of the between-practice effects and overestimation of the standard errors of the within-subject effects. Generalized Estimating Equations (GEE), specifically designed for correlated outcomes that can be modeled with a generalized linear model (GLM) including logistic regression, will be used. PROC GENMOD can easily accommodate GEE methods adjusting for clustering. For multivariable analyses logistic regression will be used again, with accounting for clustering. These models will allow adjustment for patient and practice variables described in Section D7. We will also test the hypothesis using data from each individual time point.

**Hypothesis 2: The proportion of patients referred who GO to the patient self-management website will be larger in HI-QUIT practices (40%) compared to control practices (20%).**

Data Definitions for H2: The primary dichotomous outcome will be whether or not each referred patient goes to the website. The number who visit will be recorded by the website itself which links each visitor to their provider at login. The number referred is continuously registered directly for intervention practices and can be obtained by referral receipts for control practices (see description of information prescriptions and main outcomes above). The analysis will again be done at the patient level with adjustment for clustering within practices.

Analysis for H2: A significant challenge for this hypothesis is how to count the number of patients referred (the denominator) from control practices. For intervention practices, patients will be directly referred into the HI-QUIT system by the providers using Refer2Quit. Thus, for these HI-QUIT intervention practices, we can construct a proportion (number who GO/those who are Referred) using webserver data. However, we have chosen a control to represent a current innovation in referrals, the “information prescription.” Thus, patients will not be logged into the system and we cannot use the system to create a proportion. To calculate the denominator for the control practices, we will use the leave-behind receipts from the control “information prescription” pads to tally the number of referrals from each practice. This will allow us to calculate an exact proportion.

The main patient-level analysis will again use logistic regression to model the probability that a referred smoker goes to the website where the independent variable is the group assignment of their referring practice. Because each website links patients back to their practice, we will again use GEE methods to account for clustering within practices. The main hypothesis will be tested by whether the coefficient for treatment assignment is significant in the model corrected for clustering.

Secondary analysis: Our primary approach does have the potential for errors resulting from lost, damaged, or mis-used “information prescription” pads in the control. This would result in a differential misclassification in the control as compared to the intervention group. As much of this error would underestimate the control denominator, it would still provide a conservative estimate. However, it is true that the inherent difference in the intervention and control creates a difference in the assessment of the denominator. Thus, as a secondary analysis and as safeguard against these error sources, we will repeat the analysis using the number of patients who GO as the outcome, with careful adjustment for *patient volume, proportion of smokers, and rates of referral as assessed by the exit cards at discrete time points*. This will allow us to check for consistency of results. The secondary analysis for the number who GO will use linear regression to model the number of patients per practice who go to the website by treatment assignment adjusted as above, where the test of H2 will be the significance of the coefficient for treatment assignment.

**Hypothesis 3: The proportion of smokers who are referred who QUIT at six months will be larger among intervention compared with control because of the additional connectivity of HI-QUIT.**

Data Definitions for H3: The main dependent variable for H3 is the dichotomous outcome of patient tobacco cessation (quit). The primary independent variable is assignment to intervention or control group. We have designed a patient-level analysis around point prevalence cessation based on the following question: “Do you currently smoke cigarettes (smoked even 1 puff in the last 7 days)?”

